- Women with other causes of chronic pelvic pain including infectious, gastrointestinal, psychological disorders, fibromyalgia and chronic fatigue syndrome based on review of medical history within 1 year of first study visit
- untreated severe cervical dysplasia or other gynecologic condition*
- clinically significant abnormalities on physical or laboratory examinations that require evaluation or treatment or that would make participation unsafe.*
- Hysterectomy and bilateral salpingo-oophorectomy
- Pregnancy
- Lactation
- Allergy to albumen or botulinum toxin
- Presence of antibodies to botulinum toxin or loss of response to previous injections for any indication
- A known neuromuscular junction disorder such as myasthenia gravis or Eaton-Lambert syndrome
- History of urinary or fecal incontinence
- Known pelvic prolapse

**Eligibility will be based on a physical exam at NIH at the first study visit, as well as history and available medical records within 1 year before the study visit. Negative test results will be documented to confirm study eligibility. If the Pap and the GC and chlamydia tests were not done outside of the NIH within the previous year, or if documentation of the negative test results is not available, we will await the results of the screening tests done at the NIH before administering the study medication.*

C. Criteria for withdrawal of subjects from the study

- Inability to perform home monitoring or comply with study visit schedule
- Occurrence of an adverse event that precludes further participation in the study at the discretion of the investigator
- Subject wishes to terminate participation

- Incontinence of urine or feces, or pelvic organ prolapse occurring after injection

D. Study discontinuation

- If more than 2 subjects develop incontinence or pelvic prolapse, the study will be discontinued.

V. Study procedures

A. Screening process: Women with at least a three-month history of pelvic pain suggestive of endometriosis and who have a surgical diagnosis of endometriosis will be considered for this study. Eligible women will complete written consent via telephone interview and will complete a baseline screening questionnaire (appendix 1), one month calendar (appendix 2), and submit records confirming surgical diagnosis.

B. Pre-injection medical evaluation:

This will occur in an outpatient area at the Clinical Center and will include the following for all patients:

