1. A complete history including medical conditions, headaches, depression, reproductive health history regarding sexually transmitted diseases, gynecologic conditions, menstrual history, contraceptive use, current hormonal treatment for endometriosis, and pregnancy history.
2. A physical examination including a pelvic exam. The presence of pelvic muscle spasm will be assessed as part of the screening evaluation by study gynecologist.
3. Administration of standardized questionnaires to assess:
 - The presence and severity of dysmenorrhea, deep dyspareunia, and non-menstrual pelvic pain (Standardized Pelvic Pain Questionnaire). A visual analogue assessment will also be performed (Brosens,[16]) (Appendix 3)
 - The quality of life (Endometriosis Health Profile-30) will also be assessed (Jones, [17]) (Appendix 4)
 - Pelvic floor distress inventory (Barber,[29]) (Appendix 5)
 - Patient-Reported Outcomes Measurement Information System (PROMIS ®) measures of health for Anxiety, 7 item measure, Depression, 8 item measure, Fatigue, 4 item measure, Sleep Disturbance, 4 item measure [25](Appendix 6). Patient responses to the questionnaires will not be routinely reviewed during clinic visits. Therefore, we have asked the patient, to communicate directly with the study team if, at any time during her participation, she feels concerned about her mood (anxiety or depression). If a concern is identified in speaking with the patient or reviewing patient responses, the potential for additional services will be discussed.
 - Rome criteria III for Irritable Bowel Syndrome[19](Appendix 14)
 - Painful Bladder Syndrome (Parsons, [20])(Appendix 15)

- SF 36 Health Survey (Appendix 16)
 - Oswestry Disability Index (Appendix 17)
 - BPI body territories list (Appendix 18)
 - Pain Catastrophization Scale (Appendix 19)
4. Laboratory tests: CBC with differential, liver function tests, BUN, creatinine, electrolytes, sed rate, thyroid panel, ANA, Rheumatoid factor, and CPK (15 ml), Pap smear, urinalysis, urine culture, and PCR screening for gonorrhea and Chlamydia at the Clinical Center. The following laboratory tests will occur in the morning with the patient fasting: Fasting lipid panel, fasting glucose, HbA1C, CRP, am cortisol, and DHEAS. The fasting and other blood tests may be drawn on the day of other study procedures or on a separate day, at the participant's convenience.

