They will be offered a botulinum toxin injection at 1 month after the first injection, and will return for follow-up clinic visit scheduled at that time. At that visit, the prior month's pain symptoms and use of hormonal treatments and pain medications will be reviewed, and a gynecological examination performed. At the one month visit, several questionnaires will be completed, including: Botulinum toxin patient response inventory (Appendix 10), Standardized Pelvic Pain questionnaire, standardized endometriosis QOL questionnaire, Rome criteria III for Irritable Bowel Syndrome, Painful Bladder Syndrome and PROMIS HRQL measures of sleep, fatigue, anxiety and depression, BPI body territories list, SF 36 Health Survey, Oswestry Disability Score, and pain catastrophization scale. For those opting for a second injection, this will be done as described below.

After the 1-month visit, the patient will be contacted every three months for up to 1 year, to determine how long any effects may have lasted.

E. Second injection

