1. Improvement in pain – a binary measurement of improvement/no improvement will be used.

Secondary outcome:

1. Need for re-injection at 1 month, as a binary measurement of yes/no
2. Change in Pelvic pain: pain visual analog score
3. Botulinum toxin patient response inventory
4. Standardized Pelvic Pain questionnaire
5. Standardized QOL questionnaire
6. Change in pain medication usage
7. Change in sensitization measures
8. Change in sleep, fatigue, depression or anxiety
9. Rome criteria III for Irritable Bowel Syndrome
10. Painful Bladder Syndrome
11. Change in SF 36 Health Survey
12. Change in Oswestry Disability Score
13. Change in Allostatic load
14. Change in BPI body territories list
15. Association of Pain catastrophization scores with less response to treatment

B. Sample size determination and data analysis

Most women with endometriosis interested in participating in this study of botulinum toxin

versus placebo will be on other treatment (hormones, analgesics, etc). It is unreasonable to expect them to discontinue other treatments for this study, albeit for a short time. A stratified design to account for all different types of potential treatments would be costly and time-consuming and would make it difficult to recruit subjects, especially in the no treatment arm. The randomization itself should take care of all known and unknown confounders. We expect no significant differences in the use of hormones, and other factors between groups. We will not exclude women on hormones.

We will collect information on the use of hormones and all other medications during the study. Furthermore, we will inform patients that they should not initiate or stop hormone therapy from study initiation till the one month follow-up for the primary endpoint. We will monitor women for changes in hormone and other medication use throughout the study.

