It is expected that 70% of women receiving active botulinum toxin and 20% of those receiving placebo will report improvement in their pelvic pain at one month. These estimates are from studies of botulinum toxin for back pain and are derived from a report on the effectiveness of botulinum toxin [30]. A sample size of 14 women per group will be required for detecting benefit with 80% power using two-tailed test of significance at $\alpha = 0.05$. We initially allowed for 5% drop-outs/ incomplete follow up. By the time 26 participants had been enrolled, there had been 2 withdrawals from the study. To assure an adequate number of participants completing the full one-year post injection study period, the total accrual ceiling is being raised to 35. Allowing 30 participants to be randomized will provide adequate numbers for analysis should a randomized participant fail to complete the study. Data from all randomized subjects (including withdrawals after randomization) will be included in the analyses.

The primary outcome measure, presence/absence of improvement will be evaluated with Fisher's exact test with somewhat improved and improved a lot considered as improvement, and stayed the same, somewhat worsened and worsened a lot as no improvement.

Secondary outcomes of categorical nature will also be analyzed using Fisher's exact tests. All other continuous variables collected at baseline and follow-up visits, including VAS for pain, improvement and weakness, as well as length of time of benefit, maximal benefit, weakness and maximal weakness, will be compared using t-tests or paired t-tests, as appropriate.

Frequency of side effects and weakness will be tabulated and compared by Fisher's exact test. Hormonal and pain medication variables will be compared between groups and analyses will be adjusted accordingly and as necessary. A $p < 0.05$ will be considered statistically significant. Analysis will be done as intent to treat.

VIII. Event Characterization and Reporting to the IRB, Clinical Director (CD), and Sponsor

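### Categorical secondary outcomes go to an unstratified Fisher's exact test that makes no use of recorded baseline status, so women without the syndrome at entry dilute the comparison

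*Combined protocol and SAP*

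**What the plan says.** Section VII.A lists 15 secondary outcomes. Eight are worded as changes (2, 6, 7, 8, 11, 12, 13 and 14). The pelvic pain questionnaire (4), "Rome criteria III for Irritable Bowel Syndrome" (9) and painful bladder (10) are listed by name only.

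Section VII.B gives the method: "Secondary outcomes of categorical nature will also be analyzed using" Fisher's exact tests. The variable that enters the table is not defined. Continuous variables measured at baseline and follow-up get t-tests or paired t-tests; categorical variables have no counterpart that uses baseline. The only adjustment named is for hormonal and pain medication.

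The baseline information exists. Section V.B records before injection "The presence and severity of dysmenorrhea, deep dyspareunia, and non-menstrual pelvic pain", along with the irritable bowel and painful bladder questionnaires. Section V.D repeats them at one month, including "Rome criteria III for Irritable Bowel Syndrome, Painful Bladder Syndrome".

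Section IV.B excludes "Women with other causes of chronic pelvic pain including infectious, gastrointestinal, psychological disorders", which bears on how many women can be positive for irritable bowel at entry.

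**The concern.** A woman who does not have a syndrome at entry cannot show relief from it. In a two-by-two table of arm by presence at one month, she falls in the same cell as a woman whose syndrome cleared after injection. If the table instead counts women who resolved, out of all randomized, she falls in the same cell as a woman whose syndrome persisted. Either way she adds noise and carries no information about relief.

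The protocol makes such women likely:

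- Gastrointestinal causes of pain are excluded, yet the Introduction describes irritable bowel and painful bladder as common in chronic pain. Mixed status at entry is therefore plausible.
- Sections IV.A and IV.B appear to admit women with a hysterectomy who keep their ovaries. They cannot report menstrual pain in either arm.
- Section V.C limits pregnancy tests on the injection day to sexually active women, so it foresees some who are not. They may report no dyspareunia.

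At stake is whether about 30 women can say anything about relief of these syndromes, and whether a reader can separate relief from prevalence at entry.

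**Working it through.** **Inputs from the plan (Sections VII.B and IX.A).** Significance level: "A $p < 0.05$ will be considered statistically significant". Rates: "It is expected that 70% of women receiving active botulinum toxin and 20% of those receiving placebo will report improvement". Size: "A sample size of 14 women per group will be required for detecting benefit with 80% power using two-tailed test of significance". Thirty women are to be randomized, half to each arm, so 15 per arm.

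**The plan's own figure.** With the arcsine formula, h = 2·asin√0.70 − 2·asin√0.20 = 1.055 and n = 2(1.960 + 0.842)²/h² = 14.1 per group. The pooled normal formula gives 15. The stated 14 therefore reproduces. Exact power of Fisher's test at 70% versus 20% is 64.6% with 14 per group and 68.0% with 15. This figure concerns the primary outcome; the plan gives no power or prevalence for any syndrome outcome.

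**Assumptions not in the documents.** Baseline prevalence q, the same in both arms. Clearance among affected women of 70% on toxin and 20% on placebo, borrowed from the primary outcome. No new cases, unless stated.

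**Three tables, all tested with two-sided Fisher at 0.05:**

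1. Status at one month in all women: the proportion still affected is 0.30q on toxin and 0.80q on placebo.
2. Resolved among all randomized: 0.70q and 0.20q.
3. Resolved among baseline-positive women only: 0.70 and 0.20, with the number in each arm drawn from Binomial(15, q).

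At q = 0.5, table 1 compares 0.15 with 0.40 and table 2 compares 0.35 with 0.10. Both are differences of 25 points. Table 3 compares 0.70 with 0.20, a difference of 50 points in about half as many women.

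Power by full enumeration:

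| q | 1: status | 2: resolved, all | 3: baseline-positive | 1 ÷ 3 |
|---|---|---|---|---|
| 10% | 0.3% | 0.2% | 0.3% | about 1 |
| 20% | 3.3% | 2.7% | 5.9% | 0.55 |
| 30% | 8.6% | 8.5% | 16.5% | 0.52 |
| 40% | 14.1% | 15.7% | 26.6% | 0.53 |
| 50% | 19.4% | 23.1% | 37.4% | 0.52 |
| 60% | 25.6% | 30.3% | 46.6% | 0.55 |
| 70% | 33.6% | 38.0% | 55.2% | 0.61 |
| 90% | 55.5% | 57.1% | 68.7% | 0.81 |
| 100% | 68.0% | 68.0% | 68.0% | 1.00 |

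**Sensitivity to the clearance rates.** With 90% versus 20%, the status test keeps 71% of the power at q = 0.5 and 96% at q = 0.9. With 50% versus 20%, it keeps 47% and 64%.

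**Stratified test, all women kept.** Within each baseline stratum, the number affected at one month in the toxin arm is hypergeometric given the margins. The test statistic is the sum over the two strata, and its null distribution is the convolution of the two hypergeometrics. By simulation, accurate to about one percentage point:

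- With 5% new cases, power is about 23%, 32%, 43% and 53% at q = 40%, 50%, 60% and 70%. The status test gives about 13%, 18%, 25% and 33%.
- At q = 0.5, power is about 38% against 20% with no new cases, and about 27% against 16% with 10% new cases.
- Type I error stays below 5%.

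**The case against.** A reader might infer that the plan tests follow-up status. The text does not say so. Fisher's test does not imply it: the primary outcome is itself a change category (improved or not) and is tested the same way. The missing word for change proves little, because outcomes 3 and 5 lack it too, and outcome 5 is also measured at both visits. This objection stands, and the point is therefore framed as an undefined variable with no use of baseline. It does not remove the point, because the other natural reading, resolved among all randomized, recovers little (19.4% to 23.1% at 50% prevalence, against 37.4% among baseline-positive women).

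Outcomes 4 and 10 are only assumed to be analysed as present or absent. The pelvic pain questionnaire also records severity, and numerical scores would fall under the t-test sentence. This stands too, so the fix is conditional.

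A reader might also infer that power is halved in general. That needs prevalence and clearance rates the documents do not give. The 70% and 20% are expected improvement in pelvic pain, taken from back-pain studies, and not clearance of a bowel or bladder syndrome within a month. Persistent pelvic pain is an entry criterion, so at least one pain type may be nearly universal, and there the loss is small. If the exclusions make irritable bowel rare, no analysis helps.

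Finally, the better test would still miss most real effects of this size across much of the range. That is true, but it does not justify discarding information already collected.

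**Conclusion.** The concern holds as a free improvement to the secondary analysis. Section VII.B leaves the categorical variable undefined and applies an unstratified test, while each woman's baseline status is on record. Under the borrowed 70% versus 20% clearance, no new cases and 15 per arm, the status test keeps a little over half the power of an analysis among baseline-positive women at 20–60% prevalence. The loss shrinks above that and vanishes at 100%. These sizes depend on the assumptions and are not properties of the trial.

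It would be wrong to read this as bias. Randomization protects type I error under either table, and Fisher's test already allows for chance imbalance in entry status. The primary outcome is unaffected. What is lost is power and a clear answer on relief, in outcomes the trial was not sized for.

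**What to change.** In Section VII.B add:

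> Any of outcomes 4, 9 and 10 analysed as present or absent will be compared between arms at the one-month visit with an exact test stratified by each woman's own baseline status, keeping all randomized women. The number resolved among women positive at baseline, and the number of new cases among women negative at baseline, will be shown by arm.

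State in the same place which items of these questionnaires are treated as categorical. Adding a word for change to the outcome list is not enough by itself, because resolved counted among all randomized women gains little.

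The cost is wording only. The answers are already collected at both visits, and keeping all randomized women agrees with the plan's intention-to-treat rule. The downside is that little can be concluded about a syndrome few women have at entry, and power stays modest for all of these outcomes.

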Women who undergo a second injection at the 1 month visit or at any time later within the 1 year follow-up period with the same pretreatment medication, precautions, injection technique, and follow-up as with the first injection. If this injection occurs outside of a scheduled visit, a new baseline will be established to include completion of Standardized Pelvic Pain questionnaire, standardized endometriosis QOL questionnaire, Rome criteria III for Irritable Bowel Syndrome, Painful Bladder Syndrome and PROMIS HRQL measures of sleep, fatigue, anxiety and depression, BPI body territories list, SF 36 Health Survey, Oswestry Disability Score and pain catastrophization scale. All subjects will receive botulinum toxin if a second injection is needed regardless of the randomization group. On the day of botulinum toxin injections, women who have not had a hysterectomy and who are sexually active will have a urine pregnancy test to exclude pregnancy. Women will be asked if they have had urinary or fecal incontinence or pelvic organ prolapse. Those experiencing these symptoms will be systematically assessed and, if significant, will not have an injection. Hormonal treatments and pain medications will be reviewed. One month later, several questionnaires will be completed including: Standardized Pelvic Pain questionnaire, standardized endometriosis QOL questionnaire, Rome criteria III for Irritable Bowel Syndrome, Painful Bladder Syndrome and PROMIS HRQL measures of sleep, fatigue, anxiety and depression BPI body territories list, SF 36 Health Survey, Oswestry Disability Score and pain catastrophization scale. Patients may come for an optional study visit at the one month time point.

Although only the results of the randomized injection will be used for statistical analyses, descriptive data on pain relief will be collected on the outcome of the second injection using the one month calendar of pain and medication use, and botulinum toxin patient response inventory.

F. Mid- and End-Study follow-up

Although only the results of the randomized injection will be used for statistical analyses, descriptive data on pain relief will be collected on the outcome of the additional injection using the one month calendar of pain and medication use, and the botulinum toxin patient response inventory. Additionally, at the mid-way (5-8 months) and study end (11-14 months) study visit,

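### Continuous secondary outcomes are compared by t-tests with no baseline covariate; ANCOVA of the one-month value would be modestly more precise with about 15 women per arm

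*Combined protocol and SAP*

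**What the plan says.** Section VII.B gives one rule for continuous outcomes. It covers "All other continuous variables collected at baseline and follow-up visits, including VAS for pain, improvement and weakness", together with the duration and peak of benefit and of weakness, and says that these "will be compared using t-tests or paired t-tests, as appropriate". It does not say which outcomes or contrasts get the paired version. The only adjustment it foresees is this: "Hormonal and pain medication variables will be compared between groups and analyses will be adjusted accordingly and as necessary". The outcome's own baseline value is not mentioned.

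Section VII.A words several secondary outcomes as change, for example "Change in Pelvic pain: pain visual analog score"; the PROMIS domains, SF-36, Oswestry and body territories are worded the same way. Two entries are not: the Standardized Pelvic Pain questionnaire and the "Standardized QOL questionnaire".

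The data for a baseline-adjusted analysis are already planned. Section V.B lists the pelvic pain questionnaire ("A visual analogue assessment will also be performed"), the Endometriosis Health Profile-30, PROMIS, SF-36, Oswestry and body territories before injection. Section V.D repeats these questionnaires: "At the one month visit, several questionnaires will be completed, including: Botulinum toxin patient response inventory" and the others named there. Section V.E limits inference to the first injection: "only the results of the randomized injection will be used for statistical analyses".

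**The concern.** When an outcome is measured at baseline and again after randomization, two simple t-tests are available: one on follow-up values and one on change. The first ignores baseline. The second subtracts it in full, whatever the correlation between the two visits. ANCOVA estimates how much of the baseline to remove, and over most of the plausible range of correlation it is more precise than either.

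This matters here because the groups are small and one month is the only clean randomized contrast, since all women are then offered active toxin. Intervals for pain VAS and the quality-of-life scales will be wide, and later visits cannot recover precision lost at one month.

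The wording also leaves a choice open. For the two outcomes not worded as change, either t-test fits the text, and the two estimates differ by exactly the chance baseline difference between arms. Finally, a paired t-test describes change within one arm. It does not compare toxin with placebo, and the plan does not say so.

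**Working it through.** **Inputs from the plan.** Section VII.B allows 30 women to be randomized, and Section IX.A says half receive placebo, so n = 15 per arm. The plan's only sample-size figure, 14 per group, is for the binary primary outcome (70% against 20%). It reproduces approximately: 14.1 by the arcsine formula and 15 by the pooled formula. No SD, effect size or sample size is given for any continuous outcome.

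**Assumptions.** Equal variance at both visits (SD = 1) and baseline to one-month correlation r. The documents do not give r, so I show r = 0.3, 0.5 and 0.7. I take the VAS to be repeated at one month with the pelvic pain questionnaire, because Section V.B lists them together.

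**Formulas.** The variance of the between-arm difference is proportional to:

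- follow-up-only t-test: 1
- change-score t-test: 2(1 − r)
- ANCOVA: (1 − r²) × [1 + 1/(2n − 4)]; the bracket is the cost of estimating the slope, 1 + 1/26 = 1.038

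The ratios are therefore 1.038(1 + r)/2 for ANCOVA against change, and 1.038(1 − r²) for ANCOVA against follow-up only.

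| | r = 0.3 | r = 0.5 | r = 0.7 |
|---|---|---|---|
| Variance, ANCOVA / change | 0.675 | 0.779 | 0.883 |
| Extra women the change score would need (1/ratio − 1) | 48% | 28% | 13% |
| Variance, ANCOVA / follow-up only | 0.945 | 0.779 | 0.530 |
| Extra women follow-up only would need | 6% | 28% | 89% |
| Fall in standard error against the better t-test | 3% | 12% | 6% |
| Mean 95% CI half-width (SD): change / follow-up / ANCOVA | 0.88 / 0.74 / 0.72 | 0.74 / 0.74 / 0.66 | 0.57 / 0.74 / 0.54 |
| Power for an illustrative 0.8 SD difference: change / follow-up / ANCOVA | 43 / 56 / 58% | 56 / 56 / 67% | 78 / 56 / 83% |

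The half-widths and powers come from simulation (bivariate normal, 15 per arm, 40,000 trials per setting). The simulated variance ratios agree with the formulas to within 0.01. Type I error was about 5% for all three methods. At r = 0.5, the difference detectable with 80% power is 1.06 SD with either t-test and 0.94 SD with ANCOVA.

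**Where the gain disappears.** Against follow-up only, ANCOVA breaks even when 1.038(1 − r²) = 1, that is r ≈ 0.19. Against change, it breaks even when 1.038(1 + r)/2 = 1, that is r ≈ 0.93; at r = 0.9 the ratio is already 0.987.

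**Chance imbalance.** The baseline mean difference has SD √(2/15) = 0.365. It exceeds 0.5 SD in either direction with probability 0.171, about one trial in six. A baseline difference d shifts the follow-up comparison by +r·d and the change score by −(1 − r)·d. With d = 0.5 and r = 0.5 these are +0.25 and −0.25 SD. The gap is d, whatever r is.

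**The case against.** The strongest reply is that nothing here is an error. Both t-tests are unbiased under randomization, type I error is held, and the primary analysis is not involved. Most of the named outcomes are worded as change, so baseline is already used; what is missing is a covariate. The follow-up-only comparator is an inference from two list entries that lack the word change. One of those, the pelvic pain questionnaire, may be scored in categories and would then go to Fisher's exact test. Against the better t-test the gain is only 3% to 12% in standard error over r = 0.3 to 0.7, and its true size depends on a correlation that the plan does not give. Imbalance is not a separate harm, because the variance ratios already average over it. A natural reading of the paired-test clause is within-arm use only.

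Most of this is right, and it sets the size of the point. This is a loss of efficiency, the change score is the main comparator, and the follow-up-only figures may apply to as little as one listed outcome. It does not remove the point. No section names the baseline covariate, the gain is positive across the range shown, and the plan should not leave the choice of estimate or the role of the paired test to be settled after the data are seen.

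**Conclusion.** The concern holds as a modest, inexpensive improvement to the secondary analyses. The plan uses t-tests without a baseline covariate where ANCOVA would reduce the variance by 12% to 33% against a change score. The reduction is 6% to 47% against follow-up values alone, and 6% to 22% against the better of the two. These figures rest on 15 women per arm, equal variances and r from 0.3 to 0.7. The gain is close to nil against follow-up only at r of about 0.2 or below, and against change at about 0.9. That ANCOVA is absent from the plan is certain; the exact size of the benefit is not. No bias is claimed, and the primary result is unaffected.

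**What to change.** In Section VII.B, for each continuous outcome measured at baseline and one month, compare arms with a linear model of the one-month value on arm and baseline value. Report the adjusted difference with its 95% confidence interval.

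- Keep unpaired t-tests for ratings with no baseline, such as improvement and the duration and peak of benefit. The weakness ratings belong here too if, as Section V.B suggests by not listing the response inventory, they have no baseline.
- State that paired tests within an arm are descriptive and are not evidence of toxin against placebo.
- State which scales are treated as continuous.
- Leave sensitization measures and allostatic load out of this change: Section V.D schedules no one-month value for them.

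The cost is wording and one degree of freedom per model. No data, visits or primary analysis change. The medication adjustment in Section VII.B would already need a model for these outcomes, so the extra step is small. It should be fixed before the pharmacy releases the randomization codes.

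### One p < 0.05 rule covers the primary and all 15 secondary outcomes, so with no true effect there is roughly a one-in-four to one-in-two chance of at least one 'significant' secondary result

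*Combined protocol and SAP*

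**What the plan says.** Section VII.A names one primary outcome, improvement in pain as a yes/no measure. A numbered list of secondary outcomes follows and ends at item 15, "Association of Pain catastrophization scores with less response to treatment". Item 8 alone spans four domains: sleep, fatigue, depression and anxiety.

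Section VII.B sizes the trial on the primary outcome only: "A sample size of 14 women per group will be required" "for detecting benefit with 80% power", assuming "70% of women receiving active botulinum toxin and 20% of those receiving placebo will report improvement". The primary is tested by Fisher's exact test. For the rest, "Secondary outcomes of categorical nature will also be analyzed using" the same test, continuous measures go to t-tests or paired t-tests, and side effects and weakness go to Fisher's exact test. After all of these comes one sentence: a p-value below 0.05 "will be considered statistically significant".

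Neither section names a key secondary outcome, a testing order or a multiplicity adjustment, or says that secondary results are exploratory or supportive. The one restriction is in V.E and V.F: statistical analyses use only the results of the randomized injection, and second-injection data are descriptive.

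**The concern.** The threshold sentence follows every test in VII.B and is not limited to the primary outcome. Read as written, a secondary result with p = 0.04 has the same standing as a primary result with p = 0.04. With many secondary tests, a few would be expected to cross 0.05 by chance over repeated trials of an ineffective treatment.

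What is at stake is interpretation. The protocol's opening summary says that earlier studies included too few women to establish effectiveness. In a trial of about 15 women per arm, an isolated secondary result called statistically significant could be taken as the missing evidence, and the plan gives no rule for reading it when the primary result is not significant.

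**Working it through.** **The plan's own figure.** The only numerical design claim is 14 per group for 70% versus 20%, two-sided 0.05, 80% power. The pooled normal formula gives

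n = [1.96·√(2·0.45·0.55) + 0.842·√(0.7·0.3 + 0.2·0.8)]² / 0.5² = (1.379 + 0.512)² / 0.25 ≈ 14.3, or 15 after rounding up.

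The arcsine formula gives 14.1, so the stated 14 reproduces to within one woman. It concerns the primary outcome only. The documents give no error figure for the secondary outcomes.

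**Inputs for the secondary outcomes**
- Threshold per test: 0.05 (VII.B).
- Listed secondary outcomes: 15 (VII.A).
- Women per arm: 15, from 30 randomized (VII.B) with half on placebo (IX.A).
- Pairwise correlation r between outcomes: not given; taken as 0, 0.5 and 0.7.
- Outcomes tested by Fisher's exact test: items 1, 9 and 10 appear categorical, so three, with an assumed event rate of 30%.

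**Independent tests.** P(at least one p < 0.05) = 1 − 0.95^k.
- k = 15: 1 − 0.95^15 = 53.7%.
- k = 18 (four PROMIS domains counted separately, 15 + 3): 1 − 0.95^18 = 60.3%.

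**Allowing for Fisher's exact test.** With 15 per arm and a 30% event rate in both arms, its actual false-positive rate is 1.7%, not 5%.
- 15 tests, 3 by Fisher's: 1 − 0.95^12 × 0.983^3 = 48.7%.
- 12 tests, 3 by Fisher's: 1 − 0.95^9 × 0.983^3 = 40.1%.

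**Correlated tests.** The same probability with equally correlated outcomes, by numerical integration (all tests at the full 0.05) or by simulation at 15 per arm (rows with Fisher's tests):

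| Tests | r = 0 | r = 0.5 | r = 0.7 |
|---|---|---|---|
| 15, all at 0.05 | 54% | 36% | 26% |
| 15, three by Fisher's | 49% | 35% | 25% |
| 12, three by Fisher's | 40% | 30% | 22% |
| 18, all at 0.05 | 60% | 40% | 28% |

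**Why 12 may be the right count.** Three listed items may not give a clean one-month comparison between arms.
- Item 7 (sensitization) is assessed at baseline (V.B) and study end (V.G). It is not listed for the one-month visit (V.D).
- Item 13 (allostatic load) needs fasting blood tests, which are scheduled at baseline (V.B) and at the mid-study and end visits (V.F), not at one month. From one month on, all women are offered active toxin (III).
- Item 15 relates catastrophizing to response and is not a plain contrast of toxin with placebo.

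**For comparison.** A Bonferroni threshold of 0.05/15 = 0.0033 per test would hold the independent-case chance to 1 − (1 − 0.0033)^15 = 4.9%.

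**The case against.** The strongest reply is that the plan already separates one primary outcome from the secondary ones and sizes the trial on the primary alone. The primary type I error is therefore intact, and many readers will take the word secondary to mean supportive. That is right about the primary test. It does not settle the secondary ones, because VII.B never calls them supportive and its one threshold makes no distinction.

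Second, the number of tests is not fixed by the documents. Items 7, 13 and 15 may drop out, and Fisher's test is conservative at this size. Outcomes such as pain, disability and quality of life in the same women may also be strongly correlated. All of this stands, which is why the range must start near one in four. Counting PROMIS domains or questionnaire subscales separately pushes the other way.

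A reader might infer more than the documents support:
- *That the plan declares the secondary outcomes significant, or has no hierarchy at all.* It only says how a p-value will be judged, and it does set the primary apart. What is missing is an order, adjustment or label among the secondary outcomes.
- *That the chance is at least one in three.* That holds only for low to moderate correlation, and the documents give no correlation.
- *That a non-significant primary result beside a false secondary one is the likely outcome.* The calculation here does not give that joint probability. Low power of the primary test matters when the toxin works, and significant secondary results would then not all be false.
- *That the plan intends to report secondary results as established effects.* Nothing in it says so; the rule merely permits it.

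**Conclusion.** The concern holds in a limited form. VII.B judges the primary and all 15 secondary outcomes by one unrestricted threshold. If the toxin has no effect, the chance of at least one secondary result below 0.05 is roughly one in four to one in two, against 5% for a single test. The low end rests on strong correlation (0.7) and falls to 22% if only 12 tests count. The high end rests on independence and rises to 60% with 18 tests. The correlation, the number of tests and the 30% event rate are assumptions. The design, the primary result and participant safety are unaffected. This is a cheap improvement to what the trial may claim from its secondary outcomes.

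**What to change.** In VII.B, state that the p < 0.05 rule for efficacy claims applies to the primary outcome only. Report each secondary outcome as a between-arm difference with a 95% confidence interval and label it supportive. If the sponsor wants a formal secondary claim, name one or two key secondary outcomes measured at one month and test them in fixed order, only after a significant primary result.

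Leave the side-effect and weakness comparisons as planned and unadjusted. A rule worded for the primary outcome alone, without the limit to efficacy claims, would remove the threshold from these safety comparisons for no good reason.

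The cost is one or two sentences, with no change to recruitment, visits or data. The downside is that the other secondary results can no longer be called statistically significant.
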